4.3.5 REWETTING DROPS AND OCULAR LUBRICANTS

Participants are permitted to continue using their habitual over-the-counter (OTC) drops (e.g. rewetting drops, artificial tears, eye lubricants) if they were using the product prior to their

participation in the study. Participants will be instructed not to start using any new OTC products for the study duration.

4.3.6 ORDERING CONSUMABLES

CORE will order contact lenses and contact lens care systems (as applicable) for each participant. The sponsor will supply one iLux® device and sufficient Smart Tips for use in this study.

4.3.7 DISPOSING OF CONSUMABLES

Unused Smart Tips will be returned with the iLux® device at the end of the study.

4.3.8 PRODUCT ACCOUNTABILITY

Accountability logs will be kept to include the number of lenses and lens care system bottles received, dispensed, unused. Accountability logs will also kept to document the number of Smart Tips used and returned to sponsor (if applicable). All products dispensed to participants will be recorded in the study binder.

4.4 SCHEDULED AND UNSCHEDULED VISITS

4.4.1 STUDY VISITS

This study has a total of 4 study visits, including the screening visit. The total time commitment for this study for the treatment group is 3.5 hours. The total time commitment for the control-treatment group is 4.0 hours. Participants randomized to the treatment group will be involved in the study for three months. Participants randomized to the control-treatment group will be involved in the study for four months. Table 4 summarizes the study visits.

Table 4: Summary of visit codes

Visit #	Day/s	Visits	Duration (hours)
For all participants			
Visit 1	0	Screening	1.0
For participants randomized to the treatment group			
Visit 2A	0	iLux® treatment	0.5
Visit 3A	23 - 37 days after Visit 1	1 month follow-up	1.0
Visit 4A	83 - 97 days after Visit 1	3 month follow-up & study exit	1.0
For participants randomized to the control-treatment group			
Visit 2B	23 - 37 days after Visit 1	Assessment & iLux® treatment	1.5
Visit 3B	23 - 37 days after Visit 2	1 month follow-up	1.0
Visit 4B	83 - 97 days after Visit 2	3 month follow-up & study exit	0.5

4.4.2 SCREENING (VISIT 1)

All participants who sign the informed consent letter will be assigned a study ID number. The investigator will determine participant eligibility using the inclusion and exclusion criteria. Ineligible participants will be discontinued from the study.

Participants will be instructed to refrain from the following for at least 12 hours before the screening visit:

- Used any ocular lubricants, artificial tears, emollients or liposomal sprays
- Using any eye make-up or facial cosmetics around their eyes
- Rubbing their eyes
- Swimming in a chlorinated pool

If participants attend the screening visit having used any of the products or performed any of the tasks listed above, they will be advised to reschedule their screening visit.

The following procedures will be conducted:

1. The participant is expected to attend the screening / baseline visit having refrained from CL wear for at least 12 hours. Participants are expected to bring a new pair of their habitual contact lenses and habitual solutions (if applicable)

2. The participant will be required to read and sign an Informed Consent Letter prior to enrollment. When the participant has signed the consent form, the participant will be considered enrolled in the study.
3. Participant demographics and medical history (age, sex, medical conditions, medications, allergies, management of dry eye symptoms).
4. Contact lens history: collect information regarding the participant's habitual CLs and lens care systems (if applicable). Also collect information on the participant's CL wear habits:
 - a. Average total wear time (number of days per week, number of hours per day)
 - b. Average comfortable wear time (number of hours per day).
5. The participant will complete the CLDEQ-8 questionnaire, SPEED questionnaire and OSDI questionnaire.
6. Monocular & binocular distance logMAR visual acuity (high contrast, high illumination) with habitual spectacles.
7. Non-invasive tear break-up time.
8. Lipid layer assessment (LipiView II)
9. Meibomian gland secretion assessment using the Meibomian Gland Evaluator.
10. Meibomian gland imaging of the upper and lower eyelids to determine meibomian gland drop out;
11. Ocular health assessment, including ocular surface staining.
12. Rinse eyes with saline to flush out any residual stain prior to lens insertion.
13. The participant inserts a new pair of their habitual contact lenses.
14. Contact lens fit assessment:
 - a. Monocular & binocular distance logMAR visual acuity (high contrast, high illumination)
 - b. Lens wettability
 - c. Lens deposition
 - d. Centration
 - e. Movement
 - f. Tightness (push-up test)
 - g. Overall fit
15. After the lenses have been on eye for 10 minutes, pre-lens tear breakup time will be assessed.
16. The investigator will confirm that the participant meets the eligibility specifications set out in the inclusion criteria and exclusion criteria and is eligible to continue in the study.

17. If the participant meets all the inclusion criteria and none of the exclusion criteria, the participant will be randomized.
18. If the participant is randomized to the control-treatment group, the participant is advised to continue wearing their contact lenses on average ≥ 6 hours per day, 4-7 days per week until their next scheduled visit and to refrain from using any new OTC products or medications to manage their dryness and/or contact lens discomfort symptoms.
19. If the participant is randomized to the treatment group, the participant will immediately proceed to Visit 2.

The remaining visits outlined are separated according to treatment group assignment.

4.4.3 TREATMENT GROUP

4.4.3.1 ILUX® TREATMENT (VISIT 2A)

Visit 2 occurs immediately after Visit 1 for participants that have been randomized to the treatment group. The following procedures will be conducted:

1. The participant will remove their contact lenses.
2. The participant's eyelids will be cleaned by the investigator.
3. The iLux® treatment will be administered to both eyes by the investigator.
4. A slit lamp biomicroscope examination will be performed as a safety check.
5. The participant will be provided with verbal and written instructions on how to complete blinking exercises. One round of blinking exercises will be completed with the investigator to ensure the participant understands the instructions.
6. Monocular & binocular distance logMAR visual acuity (high contrast, high illumination) with habitual spectacles as a safety check.

4.4.3.2 1 MONTH FOLLOW-UP (VISIT 3A)

Participants will attend this visit 23-37 days after iLux® treatment administered at Visit 2. Participants will attend this visit wearing a new pair of their habitual CLs for ≥ 4 hours prior to the visit. Participants who attend not meeting this criteria will be rescheduled (unless they report problems when wearing their lenses). The following procedures will be conducted:

1. Review medical history (changes in medication, adverse events)
2. Collect information on participant's CL wear habits:
 - a. Average total wear time (number of days per week, number of hours per day)

- b. Average comfortable wear time (number of hours per day).
3. The participant will complete the CLDEQ-8 questionnaire, SPEED questionnaire and OSDI questionnaire.
4. Monocular & binocular distance logMAR visual acuity (high contrast, high illumination) with habitual CLs.
5. Assess pre-lens tear film break-up time.
6. The participant will remove their CLs.
7. Meibomian gland secretion assessment using the Meibomian gland evaluator.
8. Ocular health assessment including ocular surface staining.
9. The participant will be allowed to reapply their habitual CLs or wear their own spectacles. Monocular & binocular distance logMAR visual acuity (high contrast, high illumination) with visual correction.

4.4.3.3 3 MONTH FOLLOW-UP VISIT AND STUDY EXIT (VISIT 4A)

Participants will attend this visit 83-97 days after iLux® treatment administered at Visit 2. Participants will attend this visit wearing a new pair of their habitual CLs for ≥ 4 hours prior to the visit. Participants who attend not meeting this criteria will be rescheduled (unless they report problems when wearing their lenses). The following procedures will be conducted:

1. Review medical history (changes in medication, adverse events)
2. Collect information on participant's CL wear habits:
 - a. Average total wear time (number of days per week, number of hours per day)
 - b. Average comfortable wear time (number of hours per day).
3. The participant will complete the CLDEQ-8 questionnaire, SPEED questionnaire and OSDI questionnaire.
4. Monocular & binocular distance logMAR visual acuity (high contrast, high illumination) with habitual CLs.
5. Assess pre-lens tear film break-up time
6. The participant will remove their CLs.
7. Meibomian gland secretion assessment using the Meibomian gland evaluator.
8. Ocular health assessment including ocular surface staining.
9. The participant will be allowed to reapply their habitual CLs or wear their own spectacles. Monocular & binocular distance logMAR visual acuity (high contrast, high illumination) with visual correction.
10. Study exit documentation and remuneration.

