2 OBJECTIVES

The objectives of this clinical trial are:

- To assess eye dryness symptoms (using the SPEED questionnaire) at 1- and 3-months post iLux® treatment;
- To assess Meibomian gland secretions (by expression using the Meibomian Gland Evaluator) at 1- and 3-months post iLux® treatment.

Primary endpoint:

- Changes in SPEED questionnaire score at 1 month.

Secondary endpoints:

- Meibomian gland secretion (assessments will be reported as meibomian gland scores (MGS));
- Pre-lens tear break-up time;
- Reported average wear time and comfortable wear time.

Exploratory endpoint:

- Changes in symptoms, determined using CLDEQ-8 and OSDI questionnaires, at 1- and 3-months, and SPEED at 3 months post iLux® treatment.

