4.1.2 RANDOMIZATION

A randomization schedule will be generated using a web-based program: (www.randomization.com). The final study randomization schedule will be generated by CORE's Data Team Leader and provided to the research assistants for the study. Study investigators will remain masked to the randomization schedule until the study is completed and the database is locked.

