4.1.3 MASKING

There will be no masking in this study.

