4.4.4 CONTROL-TREATMENT GROUP

4.4.4.1 ASSESSMENT AND ILUX® TREATMENT (VISIT 2B)

Participants will attend this visit 23-37 days after Visit 1. Participants will attend this visit wearing a new pair of their habitual CLs for ≥ 4 hours prior to the visit. Participants who attend not meeting this criteria will be rescheduled (unless they report problems when wearing their lenses). The following procedures will be conducted:

1. Review medical history (changes in medication, adverse events)
2. Collect information on participant's CL wear habits:
 - a. Average total wear time (number of days per week, number of hours per day)
 - b. Average comfortable wear time (number of hours per day).
3. The participant will complete the CLDEQ-8 questionnaire, SPEED questionnaire and OSDI questionnaire.
4. Monocular & binocular distance logMAR visual acuity (high contrast, high illumination) with habitual CLs.
5. Assess pre-lens tear film break-up time.
6. The participant will remove their CLs.
7. Meibomian gland secretion assessment using the Meibomian gland evaluator.
8. Ocular health assessment including ocular surface staining.
9. Confirm the participant is suitable to receive iLux® treatment.

If the participant is suitable to receive treatment, the following procedures will be conducted:

1. The participant will remove their contact lenses.
2. The participant's eyelids will be cleaned by the investigator.
3. The iLux® treatment will be administered to both eyes by the investigator.
4. A slit lamp biomicroscope examination will be performed as a safety check.
5. The participant will be provided with verbal and written instructions on how to complete blinking exercises. One round of blinking exercises will be completed with the investigator to ensure the participant understands the instructions.
6. Monocular & binocular distance logMAR visual acuity (high contrast, high illumination) with habitual spectacles as a safety check.

4.4.4.2 1 MONTH FOLLOW-UP VISIT (VISIT 3B)

Participants will attend this visit 23-37 days after iLux® treatment administered at Visit 2. Participants will attend this visit wearing a new pair of their habitual CLs for ≥ 4 hours prior to the visit. Participants who attend not meeting this criteria will be rescheduled (unless they report problems when wearing their lenses). The following procedures will be conducted:

1. Review medical history (changes in medication, adverse events)
2. Collect information on participant's CL wear habits:

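### At the 1-month visits behind the only randomised comparison, the self-reported primary SPEED score follows adverse-event and comfort questions in an unmasked trial; listing the questionnaires first would be a minor, free improvement.

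*Combined protocol and SAP*

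**What the plan says.** Section 2 names the primary endpoint as "Changes in SPEED questionnaire score at 1 month". Section 4.5.3.2 describes SPEED as a symptom questionnaire scored 0 to 28. Section 4.1.3 states: "There will be no masking in this study".

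The 1-month visits are 3A for the treated arm (4.4.3.2) and 2B for the control arm (4.4.4.1). Both begin with a review of medication changes and adverse events. Step 2 reads "Collect information on participant's CL wear habits" and covers total and comfortable wear time. Step 3 reads "The participant will complete the CLDEQ-8 questionnaire, SPEED questionnaire and OSDI questionnaire". Visits 4A, 3B and 4B open with the same three steps. At Visit 1 (4.4.2), history and wear habits also come before the questionnaires.

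Section 10.1 gives one between-group comparison: 1 month after treatment against 1 month without treatment.

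**The concern.** A participant's own rating of dryness is the primary measure, and there is no sham and no masking. Just before giving that rating, the participant has talked with staff about problems since the last visit and about how many hours the lenses stay comfortable. If that talk differs between arms, in substance or in tone, it can colour the SPEED answers differently in each arm. A difference of that kind would enter the randomised comparison and could not be separated afterwards from an effect of iLux. The plan could avoid this source of influence simply by taking the questionnaires first.

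**Working it through.** **The plan's own figures.** The plan gives no figure for this effect. Its sample size (4.2.1) reproduces. For a standardised difference of 1.0, two-sided alpha 0.05 and 90% power, the independent t-test needs 22.02 per arm, rounded up to 23. Then 2 × 23 = 46, and 46 / 0.90 = 51.1, rounded up to 52. Reordering steps changes none of these inputs, so there is no corrected number to report.

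**Order of steps at the visits that feed the comparison.**

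| Visit | Section | History / adverse events | Wear time | Questionnaires | Related later step |
|---|---|---|---|---|---|
| 1, both arms | 4.4.2 | step 3 (history) | step 4 | step 5 | randomisation, step 17 |
| 3A, treated | 4.4.3.2 | step 1 | step 2 | step 3 | none |
| 2B, control | 4.4.4.1 | step 1 | step 2 | step 3 | suitability check, step 9 |

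**What cancels and what does not.** Write the observed mean change in an arm as

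change = true change + (o1 − o0) + c

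Here o0 and o1 are the effects of asking in this order at baseline and at 1 month, and c is any effect of what is said, or how, in that arm at 1 month.

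- Between arms, o1 − o0 is common and drops out. The difference is the true effect + (c treated − c control). The order effect also drops out if 1-month scores are compared instead of changes.
- Baseline cannot correct for c. The Visit 1 questions are asked before randomisation and carry no arm-specific content.
- Within an arm, o1 − o0 remains. It is small only if baseline and follow-up use the same order. This is the reason to change all visits together, since 10.1 also plans comparisons with baseline.

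**Can c differ by arm?** The listed topics are identical. The answers need not be: at 3A the period under review includes lid cleaning and iLux, and at 2B it includes neither. Manner could differ too. The plan says "The iLux® treatment will be administered to both eyes by the investigator", so at least the person treating knows the arm. The documents do not name who asks steps 1 and 2, say whether they are asked by interview, or say whether the listed order is binding.

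**The case against.** The strongest case against acting is that the two arms follow the same order with the same wording, as the table shows, and that an arm-specific effect of the conversation is inferred rather than documented. The first part stands and is why the point is minor. The second stands in part: the documents do not show that staff question the arms differently, but what there is to discuss at 3A and 2B does differ.

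The plan might also be read as keeping investigators masked, because 4.1.2 says "Study investigators will remain masked to the randomization schedule until the study is completed and the database is locked". That conflicts with 4.1.3 and cannot hold for whoever gives the treatment, so it offers little protection.

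A further objection is that open-label expectation is probably far more important than a short interview. This is a fair judgement, though the documents quantify neither. It limits the value of the change but is no reason to leave a free one unmade.

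At Visit 2B a reader might infer that control participants raise their scores to secure treatment because staff must "Confirm the participant is suitable to receive iLux® treatment". That check is step 9, already after the questionnaires. Controls know from their allocation that treatment is due at that visit. This is expectation, and moving step 3 would not alter it.

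**Conclusion.** The point holds as a minor matter of conduct. At Visits 3A and 2B the primary score is taken after questions whose content, and possibly manner, can differ by arm in an unmasked trial. The other follow-up visits bear on within-group, pooled or exploratory results, not on the randomised primary comparison.

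The documents do not support three stronger readings that a reader might draw.

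- **That the order favours iLux.** The direction is not established. Section 6 lists burning, stinging, itching and foreign body sensation among possible effects of treatment. Recalling these just before SPEED could raise treated scores.
- **That the size can be put as a false-positive rate.** With 23 per arm (44 df, noncentrality = shift in SD × √(23/2)), an assumed differential shift of 0.1, 0.2, 0.3 or 0.5 SD gives a two-sided rate of 6.3%, 10.2%, 16.9% or 38.2% in place of 5%. These rates apply to any differential reporting bias, including participants' knowledge of their arm. Nothing in the documents ties any of these shifts to the order of steps.
- **That reordering would remove the bias.** Participants would still know their arm. Staff must also check the 4-hour lens-wear condition, with its exception for reported lens problems, so some discussion may precede the questionnaires in any case.

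The conclusion assumes that steps 1 and 2 are asked in person and in the listed order, which the plan implies but does not state.

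**What to change.** In 4.4.3.2 and 4.4.4.1, make self-completion of the questionnaires the first listed step, before the medication, adverse-event and wear-time questions. For consistency, do the same in 4.4.3.3, 4.4.4.2 and 4.4.4.3, and directly after consent in 4.4.2, so that baseline and follow-up share one order. State that the listed order is to be followed. Putting SPEED ahead of CLDEQ-8 is optional.

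The cost is an edit to the step lists. It adds no visit time, staff, participants or procedures and leaves the sample size unchanged. Sections 4.1.2 and 4.1.3 should be reconciled in the same edit.

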4.4.4 CONTROL-TREATMENT GROUP

4.4.4.1 ASSESSMENT AND ILUX® TREATMENT (VISIT 2B)

Participants will attend this visit 23-37 days after Visit 1. Participants will attend this visit wearing a new pair of their habitual CLs for ≥ 4 hours prior to the visit. Participants who attend not meeting this criteria will be rescheduled (unless they report problems when wearing their lenses). The following procedures will be conducted:

1. Review medical history (changes in medication, adverse events)
2. Collect information on participant's CL wear habits:
 - a. Average total wear time (number of days per week, number of hours per day)
 - b. Average comfortable wear time (number of hours per day).
3. The participant will complete the CLDEQ-8 questionnaire, SPEED questionnaire and OSDI questionnaire.
4. Monocular & binocular distance logMAR visual acuity (high contrast, high illumination) with habitual CLs.
5. Assess pre-lens tear film break-up time.
6. The participant will remove their CLs.
7. Meibomian gland secretion assessment using the Meibomian gland evaluator.
8. Ocular health assessment including ocular surface staining.
9. Confirm the participant is suitable to receive iLux® treatment.

If the participant is suitable to receive treatment, the following procedures will be conducted:

1. The participant will remove their contact lenses.
2. The participant's eyelids will be cleaned by the investigator.
3. The iLux® treatment will be administered to both eyes by the investigator.
4. A slit lamp biomicroscope examination will be performed as a safety check.
5. The participant will be provided with verbal and written instructions on how to complete blinking exercises. One round of blinking exercises will be completed with the investigator to ensure the participant understands the instructions.
6. Monocular & binocular distance logMAR visual acuity (high contrast, high illumination) with habitual spectacles as a safety check.

4.4.4.2 1 MONTH FOLLOW-UP VISIT (VISIT 3B)

Participants will attend this visit 23-37 days after iLux® treatment administered at Visit 2. Participants will attend this visit wearing a new pair of their habitual CLs for ≥ 4 hours prior to the visit. Participants who attend not meeting this criteria will be rescheduled (unless they report problems when wearing their lenses). The following procedures will be conducted:

1. Review medical history (changes in medication, adverse events)
2. Collect information on participant's CL wear habits:
 - a. Average total wear time (number of days per week, number of hours per day)
 - b. Average comfortable wear time (number of hours per day).
3. The participant will complete the CLDEQ-8 questionnaire, SPEED questionnaire and OSDI questionnaire.
4. Monocular & binocular distance logMAR visual acuity (high contrast, high illumination) with habitual CLs.
5. Assess pre-lens tear film break-up time
6. The participant will remove their CLs.
7. Meibomian gland secretion assessment using the Meibomian gland evaluator.
8. Ocular health assessment including ocular surface staining.
9. The participant will be allowed to reapply their habitual CLs or wear their own spectacles. Monocular & binocular distance logMAR visual acuity (high contrast, high illumination) with visual correction.

4.4.4.3 3 MONTH FOLLOW-UP VISIT & STUDY EXIT (VISIT 4B)

Participants will attend this visit 83-97 days after iLux® treatment administered at Visit 2. Participants will attend this visit wearing a new pair of their habitual CLs for ≥ 4 hours prior to the visit. Participants who attend not meeting this criteria will be rescheduled (unless they report problems when wearing their lenses). The following procedures will be conducted:

1. Review medical history (changes in medication, adverse events)
2. Collect information on participant's CL wear habits:
 - a. Average total wear time (number of days per week, number of hours per day)
 - b. Average comfortable wear time (number of hours per day).
3. The participant will complete the CLDEQ-8 questionnaire, SPEED questionnaire and OSDI questionnaire.
4. Study exit documentation and remuneration.

